#### 5.10 Retreatment

[figure not shown]
After treatment on day 1, subjects will receive a second treatment based on meeting the following criteria at the day 180 visit:

- Allergan decision and written notification to study sites allowing a second treatment
- Subject has presence of bilateral masseter muscle hypertrophy of at least marked (grade 4), as measured by the investigator using the MMPS.
- Females of childbearing potential must have a negative urine pregnancy test prior to treatment.

The second treatment is only allowed at the day 180 visit. Retreatment is prepared and administered in the same manner as described in Sections 5.1 to 5.9. Subjects will receive the same treatment at day 180 as they received at day 1.

- **6** Response Measures and Summary of Data Collection Methods
- **6.1** Efficacy Measures
- 6.2 Primary Efficacy Measure
- lower facial volume (cm³) calculated from VECTRA M3 digital photography system 3D image models (see Attachment 12.1.2)
- 6.3 Secondary Efficacy Measure
- investigator's assessment of MMH using the MMPS (5 grades: 1 = minimal, 2 = mild, 3 = moderate, 4 = marked, 5 = very marked; see Attachment 12.1.1)

## 6.5 Other Study Supplies

The following will be provided by Allergan:

• temperature recording device for monitoring refrigerator's temperature

will provide the photography system for the dental photographs to the dentists and the VECTRA M3 digital photography system and corresponding equipment.

The following will be provided by the site:

- cotton pads and makeup remover
- alcohol wipes
- medical gloves
- urine pregnancy test kits with minimum sensitivity of 25 IU/mL
- sterile surgical marker pens
- appropriately sized sterile needles and syringes for study treatment reconstitution and injection

- sterile saline (0.9% without preservative)
- refrigerator to store study treatment kits according to the Study Manual
- covered container for discarded medical waste materials (sharps box)
- internet connection (high-speed connection for electronic case report form completion)

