The present study includes CT and dental examinations developed by Allergan with input from consultants and specifically designed to identify potential effects of BOTOX treatment of MMH on the mandible and teeth. The CT scan captured by a CT technologist will be transferred to a central reader, who will review it to assess for changes in lower facial shape (masseter muscle volume, bigonial width, mandibular flare angle, and gonial angle) as well as relevant indicators of change in bone structure (mandibular condylar head shape, mandibular condylar cortical surface, mandibular condylar head, mandibular condylar position, glenoid fossa/eminence, and cortical thickness under the insertion point of the masseter muscle at the mandibular ramus). The dental examination will be conducted by a dentist to assess for any potential changes in dentition, occlusion, and overall oral health (Attachment 12.1.7). Both CT and dental measures will be taken at screening (considered as baseline), day 90, and at study exit (day 360 or study discontinuation).

In summary, the data obtained from this study will be used to develop a better understanding of the safety and efficacy of different dose regimens of BOTOX for the treatment of MMH.

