# 4.5.1.1 Definition of Women of (Non-)Childbearing Potential and/or Acceptable Contraceptive Methods

Women of non-childbearing potential are considered as those who are postmenopausal (at least 12 consecutive months without menstruation) or those who have had a hysterectomy or bilateral oophorectomy. For women of childbearing potential who may participate in the study, the following methods of contraception, if properly used, are generally considered reliable: oral contraceptives, patch contraceptives, injection contraceptives, male condom with intravaginal spermicide, diaphragm or cervical cap with spermicide, vaginal contraceptive ring, intrauterine device, surgical sterilization, vasectomized partner, or sexual abstinence

Contraceptive methods using Chinese traditional medicine or other herbal remedies are not considered acceptable methods of contraception in this study.

The investigator and each subject will determine the appropriate method of contraception for the subject during the participation in the study. At each visit, the investigator should discuss compliance with contraceptive use with females of childbearing potential. If a female becomes pregnant during the study, the investigator will notify Allergan immediately after the pregnancy is confirmed. The investigator will (1) notify the subject's physician that the subject was being treated with an investigational drug, and (2) follow the progress of the pregnancy. The investigator must document the outcome of the pregnancy and provide a copy of the documentation to Allergan.

If a pregnancy is confirmed after the subject has received study treatment, the subject may choose to exit the study after appropriate safety followup or to remain in the study for all safety and efficacy follow-up assessments through the end-of-study visit. However, CT will not be performed and a second study treatment will not be administered for any pregnant subject or on any subject of childbearing potential who does not demonstrate a negative urine pregnancy test immediately before each CT or prior to retreatment.

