## **6.8 Clinical Laboratory Evaluations**

No laboratory data will be collected for this study.

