## **6.9 Pregnancy Tests**

Urine pregnancy tests are performed prior to each treatment, day 90 of treatment cycle 1, and at the exit visit for females of childbearing potential. Subjects with positive pregnancy test results will be listed by treatment regimen, including urine sample collection date, days since day 1 treatment and days since most recent treatment.

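### Protocol 6.5 sets the pregnancy-test kit sensitivity at 25 IU/mL (25,000 mIU/mL), probably a 1,000-fold unit slip, and so permits an insensitive kit for the check before CT and retreatment

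*Protocol*

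**What the plan says.** Protocol 6.5 divides study supplies between the sponsor and the sites. The pregnancy kits are on the site list, with one requirement: "urine pregnancy test kits with minimum sensitivity of 25 IU/mL". No other visible section of the protocol or SAP gives a kit sensitivity or restates the unit. The analyte is not named, and the glossary (Protocol 12.2) does not define IU.

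The documents use the test result as follows:

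- Protocol 4.5.1.1 withholds CT and a second treatment from any woman of childbearing potential "who does not demonstrate a negative urine pregnancy test immediately before each CT or prior to retreatment".
- Protocol 5.10 makes it a retreatment criterion: "Females of childbearing potential must have a negative urine pregnancy test prior to treatment". The Protocol Summary and SAP 1.1 repeat this criterion.
- SAP 6.9 gives the testing schedule: "Urine pregnancy tests are performed prior to each treatment, day 90 of treatment cycle 1, and at the exit visit".
- SAP 6.8 states: "No laboratory data will be collected for this study". The visible plan therefore shows no serum test beside the urine kit.

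**The concern.** A sensitivity requirement is there to rule out inadequate kits. Because the sites supply the kits, this line is the only visible control over which ones are acceptable. Taken literally, the figure is so high that it may rule out very little.

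What is at stake is the reliability of a negative result. A woman in early pregnancy could test negative on a kit that complies with the protocol, and then have a CT or receive a second injection of the study toxin. The documents mean the test to prevent both.

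**Working it through.** The 25 IU/mL figure is a supply specification with no derivation in the plan, so there is no calculation to reproduce. The check is a unit conversion followed by a range.

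**Inputs**
- Written specification: 25 IU/mL (Protocol 6.5).
- Conversion: 1 IU = 1,000 mIU.
- Early-pregnancy urine level: not in the documents. Assumed range: 25 to 10,000 mIU/mL.

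**Step 1: convert.** 25 IU/mL × 1,000 mIU/IU = 25,000 mIU/mL.

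**Step 2: compare assumed levels with the written figure.** Share of threshold = level / 25,000.

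| Assumed level (mIU/mL) | Share of the written figure | Detection assured by a kit exactly at the limit? |
|---|---|---|
| 25 | 0.1% | No |
| 100 | 0.4% | No |
| 1,000 | 4% | No |
| 10,000 | 40% | No |

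The answer is the same across the whole assumed range. It changes only at 25,000 mIU/mL or above.

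**Step 3: size of the presumed slip.** If the m prefix was dropped, the intended figure would be 25 mIU/mL = 0.025 IU/mL, and 25 / 0.025 = 1,000. The documents never print mIU, so this explains the figure but does not amount to a discrepancy between two stated values.

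**Step 4: where the test is relied on.** Protocol 4.5.1.1 covers CT and retreatment, and Protocol 5.10 covers retreatment. SAP 6.9 also schedules a test before the first treatment.

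**The case against.** The strongest objection is that nothing in the documents contradicts 25 IU/mL. No hormone level is given, so the conversion alone does not prove an error. This stands in part: the range of early-pregnancy levels is an assumption. However, the conclusion holds at every point of a range that spans a factor of 400 (10,000 / 25).

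A second objection is that the figure sets a minimum performance, so more sensitive kits also comply. This stands in full. Nothing shows that a site would choose a kit at the written limit, and the practical risk may be small.

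A third is that the prefix was lost when the PDF was read. There is no sign of this in the line, where the m of mL is intact, but a look at the issued protocol would settle it.

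Four stronger readings are tempting, and the documents do not support them:

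- **The test decides entry to the study.** No visible entry criterion names it. SAP 6.9 sets a schedule, not an eligibility rule. The exclusion list is partly removed, so nothing can be concluded either way.
- **The test is the only safeguard.** Protocol 4.5.1.1 separately bars CT and retreatment for any pregnant subject, lists acceptable contraception, and has the investigator discuss contraceptive compliance at each visit.
- **SAP 6.9 omits a required test before the screening CT.** Protocol 1.3 says "Both CT and dental measures will be taken at screening (considered as baseline), day 90, and at study exit", and the SAP 6.9 list has no screening test. But the condition in Protocol 4.5.1.1 follows a sentence about pregnancy confirmed after treatment, so it can be read as covering post-treatment CTs only. Table 1 of the protocol, which holds the visit procedures, is not shown. This supports a query and no more.
- **Detection would come a stated number of days late.** A factor of 1,000 is log2(1,000) = 9.97 doublings, or about 15 to 30 days at an assumed doubling time of 1.5 to 3 days. The documents give no doubling time, and the figure applies only to a kit exactly at the written limit compared with one at 25 mIU/mL. The point does not rest on it.

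**Conclusion.** The point holds as a specification error to be confirmed and corrected. As written, Protocol 6.5 accepts a kit with a detection limit of 25,000 mIU/mL, and no other visible text overrides it. If early-pregnancy urine levels can lie between 25 and 10,000 mIU/mL, such a kit need not detect them, and a negative result would not do what Protocol 4.5.1.1 and 5.10 need of it. The text allows this outcome but does not impose it.

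The conversion is exact. The range of hormone levels is an assumption, and the dropped prefix, with its factor of 1,000, is an inference. The matter concerns subject safety only. It has no bearing on sample size, power or any efficacy analysis.

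**What to change.** - **Unit.** The sponsor should check the unit in Protocol 6.5 against the kit specification it intended, and correct it. The documents do not show what that specification was, so no value is proposed here.
- **Wording.** State the figure as the highest acceptable detection limit. A lower detection limit means a more sensitive kit, so a minimum sensitivity given as a concentration can be read in either direction.
- **Sites.** Tell sites of the correction and ask them to confirm that their kits meet it.
- **Query.** Reconcile SAP 6.9 with Protocol 1.3 and 4.5.1.1 on whether a test precedes the screening CT. Screening runs from day -56 to day -1 (Protocol 3), so a test on day 1 would come after that scan. If Table 1 already lists a screening test, only the SAP list needs aligning.

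The cost is one protocol line, a site notice and possibly one SAP line. The unit correction adds no procedure, staff or subjects.

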#### 6.6 Summary of Methods of Data Collection

This protocol will use electronic case report forms (eCRFs) using remote electronic data capture (EDC) through a qualified third party vendor. The data will be entered on the eCRFs on an ongoing basis throughout the study.

#### 7 Statistical Procedures

A detailed statistical analysis plan will be generated and finalized prior to the first cohort day 90 database snapshot.

For each cohort, there will be a database snapshot with key data through the day 90 visit, for the purpose of the DRC. There will be a final database lock with all study data after all subjects have completed the study (final cohort day 360). Subjects' treatment assignment will remain blinded for all site personnel, study subjects, and Allergan personnel directly involved with ongoing operational activities of the clinical study, until completion of the final database lock.

# 7.1 Analysis Populations

All efficacy analyses will be performed on the modified intent-to-treat (mITT) population as treated, consisting of all randomized subjects who received study treatment and had at least 1 follow-up visit. A per-protocol (PP) analysis will also be performed on the primary endpoint. The PP population will be defined prior to database lock. Criteria used as a guideline in determining the exclusion of subjects or data from the PP analysis include violation of key inclusion and exclusion criteria, taking prohibited medication, and receiving the incorrect treatment.

The safety analyses will be based on the safety population, which will include all subjects who receive at least 1 injection of treatment. All safety analyses will be performed with subjects analyzed by their actual treatment or regimen received on day 1.

# 7.2 Collection and Derivation of Primary and Secondary Efficacy Assessments

Efficacy results for all study visits will be summarized based on time since injection. Visit windows for all timepoints will be described in the statistical analysis plan.

Pairwise comparisons will be done between each BOTOX group and the placebo group. A pairwise comparison will also be done between a BOTOX group and the next higher dose BOTOX group. For interim analyses, subjects in the placebo group(s) from previous cohort(s) will be pooled with the placebo group from the current cohort for analysis if the results for the placebo groups are combinable. For final analysis, all subjects who received placebo will be pooled together as a total placebo group if the results for the placebo groups are combinable. Details will be specified in the Analysis Plan.

The primary efficacy variable will be the lower facial volume at day 90. The change from baseline in lower facial volume will be analyzed by analysis of variance (ANOVA) with treatment and baseline (day 1) MMPS grade as factors to assess the response between groups.

For analysis of the mITT population, the last observation carried forward (LOCF) method will be used to impute missing values. For analysis of the PP population, observed data without imputation will be used.

# 7.2.1 Primary Efficacy Variable

The primary efficacy variable, change from baseline in lower facial volume (cm^3), is calculated from VECTRA M3 digital photography system 3D image models

# 7.2.2 Secondary Efficacy Variable

The secondary efficacy variable is the investigator's assessment of MMH using the MMPS (1 = minimal, 2 = mild, 3 = moderate, 4 = marked, 5 = very marked).

#### 7.3 Hypothesis and Methods of Analysis

#### 7.3.1 Primary Efficacy Analyses

Descriptive statistics for change from baseline in lower facial volume for each study visit (sample size, mean, standard deviation, median, minimum, and maximum) will be provided by treatment regimen for all scheduled visits.

The primary efficacy analysis will be based on the mITT population. Day 90 is the primary timepoint.

The following set of hypotheses will be used to compare the BOTOX groups with placebo:

- Null hypothesis: BOTOX and placebo are equally effective in changing lower facial volume at day 90.
- Alternative hypothesis: BOTOX and placebo are not equally effective in changing lower facial volume at day 90.

[figure not shown]
The change from baseline in lower facial volume at each visit will be analyzed using an ANOVA model with treatment and baseline (day 1) MMPS grade as factors. In addition, 2-sided 95% confidence intervals for the treatment differences will be provided.

[figure not shown]
Analysis will be performed for the PP population and also based on observed data (ie, strictly data that falls within the visit windows) for the mITT population.

[figure not shown]
# 7.3.2 Secondary Efficacy Analyses

[figure not shown]
The proportion of responders will be analyzed with a responder defined as subjects who achieve an MMPS grade of  $\leq 3$ . The proportion of responders will be analyzed using Cochran-Mantel-Haenszel (CMH) tests stratified by baseline (day 1) MMPS grade.

[figure not shown]

## 7.4 Subgroup Analyses

Subgroup analyses of the primary efficacy variable will be provided by subgroups of race (Asian and non-Asian), gender, age (18 to 35 years and 36 to 50 years), and baseline (day 1) MMPS grade (4 and 5).

## 7.5 Sample Size Calculation

The sample size used in this study is determined empirically.

For each cohort, 40 subjects will be randomized to BOTOX, and 10 subjects will be randomized to placebo. Assuming the VECTRA lower facial volume is a normal distribution and the effect size is 1, a 1-sided test with 0.10 significance level will have 93% power to detect a statistically significant change in the BOTOX group compared with the placebo group. The commercial software nQuery version 6.01 procedure MTT0U-1 was used for the power calculation.

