#### Sample Size Calculation:

The sample size used in this study is determined empirically. For each cohort, approximately 40 subjects will be randomized to BOTOX and approximately 10 subjects will be randomized to placebo. Assuming the VECTRA lower facial volume is a normal distribution and the effect size is 1, a 1-sided test with 0.10 significance level will have 93% power to detect a statistically significant change in the BOTOX group compared with the placebo group. The commercial software nQuery version 6.01 procedure MTT0U-1 was used for the power calculation.

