#### 4 Study Population and Entry Criteria

#### 4.1 Number of Subjects

Based on the proposed doses, it is anticipated that approximately 200 subjects will be enrolled in the 4 planned cohorts. The actual number of subjects entering the study will be determined by the number of cohorts conducted and the number of subjects enrolled within each cohort.

Subjects will be enrolled at approximately 4 to 12 investigational sites.

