### **2.3.7 Significance Level**

The level of significance used for all statistical tests will be 0.05, 2-sided, unless stated otherwise.

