## **5. Efficacy Analyses**

Pairwise comparisons will be done between each BOTOX group and the placebo group. A pairwise comparison will also be done between a BOTOX group and the next higher dose BOTOX group.

All subjects who received placebo will be pooled together as placebo group for analyses.

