### **5.2 Primary Efficacy Analyses**

Descriptive statistics for change from baseline in lower facial volume for each study visit (sample size, mean, standard deviation, median, minimum, and maximum) will be provided by treatment regimen for all scheduled visits.

The primary efficacy analysis will be based on the mITT population. Day 90 is the primary timepoint.

The following set of hypotheses will be used to compare the BOTOX groups with placebo:

- Null hypothesis: BOTOX and placebo are equally effective in changing lower facial volume at day 90.
- Alternative hypothesis: BOTOX and placebo are not equally effective in changing lower facial volume at day 90.

The change from baseline in lower facial volume at each visit will be analyzed using an ANOVA model with treatment, and baseline MMPS grade as factors. In addition, 2-sided 95% confidence intervals for the treatment differences will be provided.

Analysis will also be performed based on observed data (ie, strictly data that falls within the visit windows) for the mITT population.

Among-group comparisons for the placebo groups will be analyzed using an ANOVA model with treatment as factor to test whether they are combinable. If the difference among the placebo groups are significant, sensitivity analysis will also be done for the primary variable using an ANOVA model with treatment, cohort number (as numeric variable) and baseline MMPS grade as factors.

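### The 93% power is computed for a 1-sided 0.10 test of 40 vs 10, a test that no readable analysis section uses; the planned 2-sided 0.05 pooled-placebo comparison has about 99%

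*Protocol*

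**What the plan says.** **Power statement.** Protocol 7.5 calls the sample size empirical. For each cohort of 40 BOTOX and 10 placebo subjects, with normal data and an effect size of 1, it states that "a 1-sided test with 0.10 significance level will have 93% power to detect a statistically significant change in the BOTOX group" compared with placebo. The Protocol Summary repeats this: "a 1-sided test with 0.10 significance level will have 93% power".

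**Planned test.**
- Protocol 7.3.1 and SAP 5.2 give the same non-directional alternative: "Alternative hypothesis: BOTOX and placebo are not equally effective in changing lower facial volume at day 90".
- Both attach 2-sided intervals to the ANOVA (treatment and baseline MMPS grade as factors): "In addition, 2-sided 95% confidence intervals for the treatment differences will be provided".
- SAP 2.3.7 fixes the level: "The level of significance used for all statistical tests will be 0.05, 2-sided, unless stated otherwise".

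**Control group.**
- SAP section 5: "All subjects who received placebo will be pooled together as placebo group for analyses". SAP section 1 plans four cohorts, so the pooled placebo group is about 4 × 10 = 40.
- Protocol 7.2 pools as cohorts accrue, provided the placebo groups are combinable: "For interim analyses, subjects in the placebo group(s) from previous cohort(s) will be pooled with the placebo group from the current cohort".
- Protocol 4.1 leaves the total open: it "will be determined by the number of cohorts conducted" and by enrolment within each.

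The SAP does not restate the power calculation, and its section 11 reports no deviations from Protocol section 7.

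**The concern.** The power statement differs from the planned primary comparison in three ways: the level (0.10 against 0.05), the sidedness (1-sided against 2-sided) and the control group (10 against about 40). The first two make the stated figure too high for the planned test and the third makes it too low, so the net effect has to be computed.

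A reader who meets 93% in the sample size section will probably take it as the power of the primary test. It is not the power of any test in the readable plan.

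The level also matters for the cohort reviews. Under Protocol 3.1 the DRC looks at efficacy as well as safety through day 90 of each cohort, when it considers retreatment and advancement. At the first review only about 10 placebo subjects exist. If efficacy is tested there, the result can depend on which of the two levels is meant.

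**Working it through.** **Inputs.** Effect size d = 1, 40 BOTOX and 10 placebo per cohort, 1-sided 0.10 (Protocol 7.5). Level 2-sided 0.05 (SAP 2.3.7). Pooled placebo of 10, 20, 30 or 40 after one to four cohorts (Protocol 7.2, SAP section 5). Assumed here: full planned numbers, no losses, no multiplicity adjustment, no difference among the cohorts' placebo groups.

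**Formula.** Two-sample t-test with a noncentral t distribution:

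ncp = d × √(n₁n₂ / (n₁ + n₂)), df = n₁ + n₂ − 2.

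Power is the probability that a noncentral t with these values exceeds the critical value (for the 2-sided test, in either tail).

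**Step 1: the stated figure.** For 40 vs 10, ncp = √(400/50) = 2.828 and df = 48. The 1-sided 0.10 critical value is 1.299, and power is 93.6%. The stated 93% is reproduced. The same groups give 87.4% at 1-sided 0.05 or 2-sided 0.10, and 79.1% at 2-sided 0.05, so the figure does rest on 1-sided 0.10.

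**Step 2: the SAP level, by size of the placebo group.** The last column uses the residual df of the planned ANOVA: total subjects (50 per cohort), minus treatment groups, minus 1 for MMPS grade.

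| BOTOX vs placebo | ncp | Power, 2-sided 0.05 (t-test df) | Power with ANOVA df |
|---|---|---|---|
| 40 vs 10 | 2.828 | 79.1% (48) | 79.1% (47) |
| 40 vs 20 | 3.651 | 94.8% (58) | 95.1% (96) |
| 40 vs 30 | 4.140 | 98.3% (68) | 98.4% (145) |
| 40 vs 40 | 4.472 | 99.3% (78) | 99.4% (194) |

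At the SAP level, power is above 93% once two cohorts' placebo groups are pooled and below it only for 40 vs 10. There the gap from the stated figure is 93 − 79 = 14 percentage points.

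**Step 3: effect detectable with 93% power at 2-sided 0.05.** 0.78 SD for 40 vs 40; 1.24 SD for 40 vs 10.

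**Step 4: what the choice of level does at 40 vs 10.** The smallest observed difference that reaches significance is t × √(1/40 + 1/10) = t × 0.3536:
- 1-sided 0.10: 1.299 × 0.3536 = 0.46 SD
- 2-sided 0.05: 2.011 × 0.3536 = 0.71 SD

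An observed benefit between 0.46 and 0.71 SD is significant under one level and not under the other.

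**Step 5: sensitivity of the 40 vs 40 figure.**
- 10% loss in each group (36 vs 36): 98.7%.
- Bonferroni split over four doses (0.0125 each; an assumption, not in the plan): 97.0%.
- d = 0.8: 94.2% (40 vs 10: 60.2%).
- d = 0.5: 59.8% (40 vs 10: 28.3%).

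**The case against.** The case for leaving the text alone has four parts.

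- **Nothing depends on the figure.** The sample size was chosen empirically, and the final comparison has more power than stated. Both points are true, and they limit the weight of the finding. They do not make the printed figure describe the planned test.
- **The sentence gives its own basis, and a use is easy to imagine.** It is framed per cohort, and a lenient 1-sided level would be plausible for the DRC's review. The DRC Charter is not among the documents, and parts of the SAP efficacy section are redacted, so this use cannot be excluded. No readable passage states it, however, and SAP 2.3.7 applies 2-sided 0.05 unless another level is stated. The finding covers the readable text only.
- **The 79% belongs to a comparison the SAP does not specify.** SAP section 5 pools placebo unconditionally. If the placebo groups differ, SAP 5.2 adds a sensitivity model with cohort number and does not fall back to one cohort's placebo. Nor does any readable text prescribe a 2-sided 0.05 test at the DRC snapshot. The 79% is therefore conditional. It remains relevant because Protocol 7.2 plans pairwise comparisons and interim pooling as cohorts accrue, and at the cohort 1 snapshot there is nothing to pool.
- **A headline of 99% is more optimistic and carries its own assumptions.** This stands in part. The restated figure needs its conditions beside it: four cohorts, no losses, no multiplicity adjustment and no cohort effect among placebo groups. It also inherits an effect size of 1, for which the protocol gives no difference in cm³ and no SD.

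**Conclusion.** The concern holds. The 93% is correct for its stated inputs, but it is not the power of any test in the readable plan. At 2-sided 0.05 and effect size 1, each dose against a pooled placebo group of 40 has about 99% power, so the final primary comparison is not underpowered. A comparison limited to one cohort's placebo group has about 79%.

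This is an inconsistency between sections, not an arithmetic error, and it should be fixed. Confidence is high for the mismatch in the readable text and for the calculations. Whether a 1-sided 0.10 test exists in redacted text or in the DRC Charter cannot be determined from these documents.

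**What to change.** Restate the power in Protocol 7.5 and the Protocol Summary at the level the SAP uses, for example:

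> At 2-sided 0.05 and effect size 1, with no losses and no multiplicity adjustment, each BOTOX dose (n about 40) against pooled placebo (n about 40, four cohorts, no cohort effect) has about 99% power, and 93% power for an effect size of 0.78. A comparison limited to one cohort's placebo group (40 vs 10: the cohort 1 day-90 snapshot, or a later snapshot if the placebo groups are not combinable) has about 79% power at effect size 1.

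If 1-sided 0.10 is intended for the DRC's cohort review, keep the 93% for that purpose, label it so, and state that level in the SAP for that review only.

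The cost is wording in two places in the protocol, plus one line in the SAP if the 1-sided level is kept. Enrolment and analysis stay as they are. The headline figure rises from 93% to about 99%, and the single-cohort figure falls to about 79%.
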